5.4. Protocol

Patients will be identified and selected upon admission. If they meet the selection criteria and confirm their willingness to participate in the study, they will be randomized in a 1:1 sequence through a mobile application specifically designed for the study by P INVESTIGA, to one of the following interventions within 48 hours of hospital arrival:

1) "ReDS-guided strategy." Each day, the clinician responsible for the patient will have access to the ReDS value and will adjust the treatment according to the study's diuretic protocol (annex 3). The responsible physician can discharge the patient if the clinical stability criteria are met, and the ReDS value is below 35% and/or a reduction of 15% or more from the admission ReDS value has been achieved. If the ReDS criteria are not met, the patient must remain hospitalized for another day until these conditions are met. Clinical stability is defined as the presence of at least 2 of the following 3 conditions: i) discharge weight lower than admission weight, ii) at least a 20% reduction in natriuretic peptide from admission, and iii) a score <2 in the Orthoedema score.

2) "Usual clinical practice strategy." The responsible physician will not have access to the ReDS values and will adjust the treatment according to their clinical judgment and local practices. Discharge can be given if the clinical stability criteria are met.

The ReDS technology has been described in detail previously (7, 8, 20). Briefly, the ReDS system consists of 2 sensors that are placed (sitting or supine) on the front (infraclavicular) and back (below the scapula) of the patient's right hemithorax and in 45 seconds accurately quantifies the proportion of fluid in the lung. The sensors are connected via 1 cable to a touchscreen monitor that easily guides the measurement process and stores this information. The accuracy of this technology has been validated with high-resolution chest computed tomography (8) and invasive hemodynamic measurements with a Swan-Ganz catheter (9). Normal ReDS values range between 20% and 35% (i.e., 20-35% of the lung would be fluid). Above 35% is considered congestive, whereas below 20% the lung would be "dry" or dehydrated.

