5.5.1 Baseline visit (within first 48 hours of hospital admission)

- Informed consent with date and signature of the patient and local investigator.
- Demographic data: race, gender, and age, and anthropometric data: weight and height.
- Complete medical history, including main comorbidities and usual medical treatment.
- Usual NYHA functional class before decompensation.
- Vital signs (blood pressure, heart rate, arterial saturation) and daily physical examination findings (weight, signs of left and right congestion).
- 12-lead ECG.
- Baseline echocardiogram (or the last available in the year before the current admission).
- Complete blood tests (renal and liver function, electrolytes, lipid profile, NTproBNP/BNP, CA125, blood count, and coagulation).
- Alternative methods for congestion analysis used by local clinical practice: lung ultrasound, VExUS, impedance, right heart catheterization.
- Measurement with the ReDS system.

5.5.2. Follow-up visits (every day during admission):

- Vital signs (blood pressure, heart rate, arterial saturation) and daily physical examination findings (weight, signs of left and right congestion).
- Measurement with the ReDS system
- Alternative methods for congestion analysis used by local clinical practice: lung ultrasound, VExUS, impedance, right heart catheterization.

5.5.3. Visit at discharge (within 24 hours before hospital discharge):

- Current NYHA functional class at discharge.
- Vital signs (blood pressure, heart rate, arterial saturation) and daily physical examination findings (weight, signs of left and right congestion).
- 12-lead ECG.
- Echocardiogram at discharge (not mandatory).
- Complete blood tests (renal and liver function, electrolytes, lipid profile, NTproBNP/BNP, CA125, blood count, and coagulation).
- Alternative methods for congestion analysis used by local clinical practice: lung ultrasound, VExUS, impedance, right heart catheterization.
- Measurement with the ReDS system
- Major interventions performed during the index admission: revascularization, electrical cardioversion, arrhythmia substrate ablation, device implantation, complications, etc.

5.5.4. First visit at HF Clinic (14 +/- 3 days after hospital discharge):

- Current NYHA functional class.
- Vital signs (blood pressure, heart rate, arterial saturation) and daily physical examination findings (weight, signs of left and right congestion).
- 12-lead ECG.

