The sample size estimation is based on the two previous studies by the group with this technology (references 19 and 20, which observed a Hazard ratio of 0.20 and 0.10 for the primary efficacy event respectively for ReDS-guided treatment) and on the average rate of the primary efficacy event (15%) of the participating hospitals during 2023. For an 80% power, a 5% alpha error, and considering a 10% subject loss rate during follow-up, 507 patients per group (1014 in total) are needed to detect a 50% reduction in the primary efficacy event (conservative estimate).

To evaluate the efficacy of the randomization process, a descriptive analysis will be performed using the chi-square test, Student's t-test, or Wilcoxon rank-sum test, as appropriate. All comparisons will be conducted according to the intention-to-treat principle. The time to the primary endpoint will be evaluated using Kaplan-Meier estimates and Cox proportional hazards models. A hierarchical analysis of the primary event with the win ratio method will also be performed. The number of patients needed to treat to prevent an efficacy event (NNT), and a safety event (NNH) will be calculated. For secondary outcomes, differences in plasma biomarker levels will be evaluated with chi-square, Fisher's exact test, t-test, and Wilcoxon rank-sum test, as appropriate. A p-value <0.05 will be considered statistically significant. The Stata program (StataCorp, Texas, USA) will be used.

Two interim analyses of the results are planned when 30% (risky estimate) and 60% (average estimate) of the sample size is reached. In addition, a steering committee of the clinical trial will be created, comprising members of recognized prestige ([name] [name], [name] [name], [name], [name], [name], [name], [name]), independent of the research team, who will ensure strict compliance with the protocol and have access to real-time event rates to detect potential futility of the intervention.

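### Section 5.6 uses baseline significance tests to evaluate the randomisation; an isolated p-value cannot show this either way (minor)

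*Protocol*

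**What the plan says.** Section 5.6 plans the baseline comparison in these words: "To evaluate the efficacy of the randomization process, a descriptive analysis will be performed using the chi-square test, Student's t-test, or Wilcoxon rank-sum test". The sentence gives a purpose (judging the randomisation), a tool (hypothesis tests between the arms) and a label (descriptive). It does not say which variables are tested, how many, how the results are read, or what follows from them.

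The section gives one general threshold: "A p-value <0.05 will be considered statistically significant". It comes later in the same paragraph, after the secondary outcomes, and is not tied to the baseline tests. No other criterion is offered.

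On allocation, section 5.4 says of the patients that "they will be randomized in a 1:1 sequence through a mobile application specifically designed for the study".

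Section 5.5.1 lists what is collected at baseline. It includes "Demographic data: race, gender, and age, and anthropometric data: weight and height", "Complete medical history, including main comorbidities and usual medical treatment" and "Complete blood tests (renal and liver function, electrolytes, lipid profile, NTproBNP/BNP, CA125, blood count, and coagulation", together with NYHA class, vital signs, congestion signs, ECG, echocardiogram and the ReDS value.

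For the primary endpoint, section 5.6 says: "The time to the primary endpoint will be evaluated using Kaplan-Meier estimates and Cox proportional hazards models". No covariates are named there.

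**The concern.** A baseline test asks whether a difference between the arms could be due to chance. If the application allocates correctly, chance is the only possible cause, so the null is true before any data are seen. A small p-value on one variable is then a chance finding, to be expected in about 1 test in 20.

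The converse also fails. A p-value above 0.05 depends on sample size and not on how strongly the variable predicts the outcome. It does not show that a strong predictor, such as natriuretic peptide, is balanced closely enough to leave the treatment comparison undisturbed.

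At stake is how the baseline table is read. Someone who takes the stated purpose at face value may report a chance difference as a weakness of the randomisation, or take a column of non-significant p-values as assurance of balance. This is a stated method joined to a purpose it does not serve, and not a detail left to the statistical analysis plan.

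**Working it through.** The protocol gives no figure on this point, so there is none to reproduce.

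**Inputs**

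- Threshold 0.05: section 5.6, taken as two-sided (sidedness is not stated).
- Arm size 507: section 5.6.
- Number of tests k: not stated. Section 5.5.1 names about 22 items or panels: five demographic and anthropometric, NYHA class, three vital signs, left and right congestion signs, ECG, echocardiogram, eight laboratory items or panels, and ReDS. Comorbidities, drugs and single analytes would add to this. Assumption: k = 20 to 30, with 10 to 40 as a wider range.
- Correlation between tests: not stated. Assumption: 0 to 0.5.

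**Step 1. Expected number of chance findings.** This is 0.05 × k, or 1.0 for k = 20 and 1.5 for k = 30.

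**Step 2. Chance of at least one p<0.05 when allocation is correct.** For independent tests it is 1 − 0.95^k. For example, k = 20 gives 1 − 0.3585 = 0.6415. For correlated tests I took k normal test statistics with a common pairwise correlation and integrated over the shared component.

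| k | independent | corr. 0.2 | corr. 0.4 | corr. 0.5 |
|---|---|---|---|---|
| 10 | 40.1% | 37.7% | 32.1% | 28.7% |
| 20 | 64.2% | 59.0% | 48.2% | 41.9% |
| 25 | 72.3% | 66.3% | 54.0% | 46.7% |
| 30 | 78.5% | 72.2% | 58.8% | 50.7% |
| 40 | 87.2% | 80.8% | 66.5% | 57.2% |

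Weight with congestion signs, and renal function with electrolytes, are plausibly correlated. The independent column is therefore the upper end.

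**Step 3. What a non-significant test tolerates.** With 507 per arm, a standardised difference stays non-significant up to about 1.96 × √(2/507) = 0.123 SD. For a predictor with an assumed log-hazard of 0.5 to 0.9 per SD, an imbalance of that size moves the hazard ratio by a factor of about exp(0.5 × 0.123) = 1.06 to exp(0.9 × 0.123) = 1.12, that is 6% to 12%.

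**Step 4. What prespecified adjustment would gain.** Assumptions: 456 evaluable per arm (507 × 0.9 = 456.3), 15% control risk and one normally distributed prognostic score in the Cox model. A simulation with 2,500 runs per setting gave this power, unadjusted then adjusted:

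| log-hazard per SD | hazard ratio 0.5 | hazard ratio 0.6 |
|---|---|---|
| 0.5 | 93.2% → 93.7% | 73.2% → 74.2% |
| 0.7 | 92.4% → 93.3% | 71.9% → 74.5% |
| 0.9 | 90.8% → 93.2% | 71.1% → 76.7% |

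Allowing for simulation error and for a separate run with the same inputs, the gain is about 1 to 3 points at the planned hazard ratio of 0.5 and about 2 to 6 points at 0.6. The low end belongs to the weaker predictors.

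**The case against.** The strongest reply is that the protocol calls this a descriptive analysis and attaches nothing to it. It contains no rule that any p<0.05 means failure, gives no number of tests and names no action. Printing p-values in a baseline table does not declare the randomisation unsound. This stands, and it limits the point to a minor one.

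Three stronger readings are tempting, and the document supports none of them:

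- A reader might infer that the trial, run as written, will more likely than not report a failed randomisation. That needs a decision rule and a number of tests, and the protocol gives neither. The percentages in Step 2 are conditional on both, and fall below one half for 20 tests at correlation 0.4.
- A reader might infer that the tests can detect nothing. That goes too far. Whether the process ran correctly is the question being asked, and many or extreme p-values could still reveal gross subversion or an allocation error. What carries no information is the isolated p<0.05.
- A reader might infer that the baseline p-values will choose the covariates of the Cox model. Nothing in the protocol says so, and no primary or secondary inference is stated to depend on these tests.

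It can also be said that covariates are commonly fixed in the statistical analysis plan, which is not at hand. That is right. Their absence from section 5.6 is not an error, and adjustment is offered here only as the better response to chance imbalance. At the planned effect, power is already above 90% in these simulations, so the gain is small.

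**Conclusion.** The point holds, as a minor one. Section 5.6 gives baseline significance tests the task of evaluating the randomisation. Under correct 1:1 allocation about 1 in 20 will be significant by chance. With 20 to 30 variables, at least one p<0.05 would appear in 64.2% to 78.5% of sound trials if the tests are independent, and in about 48% to 59% at correlation 0.4. The number of tests, their correlation and an any-significant reading are all assumptions and not protocol content. Non-significance is no assurance either: an imbalance of up to about 0.12 SD on a strong predictor would pass.

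The planned primary analysis does not change whatever these tests show. The harm is confined to misreading the baseline table, and the gain from the replacement is modest and depends on the assumed prognostic strength.

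**What to change.** In section 5.6:

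1. Remove the tests as an evaluation of the randomisation. Present baseline data by arm descriptively, without p-values; standardised differences can be added.
2. Check the allocation directly, from the log of the randomisation application.
3. In section 5.6 or the statistical analysis plan, name a few prognostic variables for the primary Cox model and adjust for them whatever the observed balance, using values recorded before allocation. Examples already collected are log natriuretic peptide, age and renal function. Add an assay term, because section 5.2 accepts either NT-proBNP or BNP. Keep the unadjusted model as a sensitivity analysis.

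The cost is a few sentences, with no extra patients, visits or measurements. The downsides are that the adjusted hazard ratio is conditional on the covariates and so is not the same quantity as the unadjusted one, and that a rule is needed for missing baseline values.

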5. METHODOLOGY

5.1. Study design (annex 1)

A randomized, single-blind, controlled, multicenter clinical trial (list of investigators and participating centers in annex 2) promoted by the researcher, which evaluates the efficacy and safety of a decongestion strategy guided by the ReDS system compared to standard clinical practice in patients admitted for decompensated heart failure.

5.2. Study population

Those adult patients meeting all the following criteria will be included:

- 1. Hospitalized due to HF as the main reason, including the presence of symptoms and signs of congestion, regardless of the left ventricular ejection fraction (LVEF).
- 2. NT-proBNP greater than 1000 pg/L or BNP greater than 300 pg/L upon admission.

Patients meeting any of the following conditions will be excluded:

- 1. Height less than 150 cm or greater than 190 cm or body mass index (BMI) less than 22 or greater than 39, conditions where the use of ReDS is not approved.
- 2. Patients requiring inotropes or vasopressors upon admission, with mechanical support, or heart transplant recipients.
- 3. Any malformation or variant affecting the right lung anatomy (e.g., a pacemaker).
- 4. Patients with any heart disease requiring a planned surgical intervention during the clinical trial (coronary disease, valve disease, or other).
- 5. Chronic kidney disease on hemodialysis.
- 6. Life expectancy less than 12 months due to non-cardiological origin.
- 7. Participation in another clinical trial with intervention.

5.3. Variables

- 1. Primary efficacy variable: combined 30-day outcome of all-cause mortality, heart failure (HF) readmission, or HF-related visits requiring diuretic treatment adjustment.
- 2. Secondary efficacy variable: individual components of the main variable, proportional change in natriuretic peptides and CA125 between admission and the first post-discharge outpatient visit, New York Heart Association functional class at the first post-discharge outpatient visit, average length of stay, cost of hospitalization for HF, and unplanned visit.
- 3. Primary safety variable: combined outcome of symptomatic systolic hypotension (<90 mmHg), electrolyte imbalances (potassium below 3 or above 5.5 meq/L), and/or worsening of renal function compared to the baseline visit at the first post-discharge outpatient visit (at least 50% reduction in glomerular filtration rate).

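### The secondary biomarker comparison is limited to tests that do not adjust for the admission value, and the quantity tested is worded in two ways; a log-scale ANCOVA would be more precise at almost no cost

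*Protocol*

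**What the plan says.** Hypothesis 2.2 (section 3) predicts, among other things, that natriuretic peptides and CA125 will fall further under ReDS guidance. Three places in the protocol decide how that comparison is made.

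- **Endpoint.** Section 5.3 lists, among the secondary efficacy variables, "proportional change in natriuretic peptides and CA125 between admission and the first post-discharge outpatient visit".
- **Test.** Section 5.6 says that, for secondary outcomes, "differences in plasma biomarker levels will be evaluated with chi-square", and adds the Fisher, t and Wilcoxon tests, with the choice among them left to what is suitable. The threshold follows: "A p-value <0.05 will be considered statistically significant".
- **Data.** Section 5.5.1, headed "Baseline visit (within first 48 hours of hospital admission)", schedules "Complete blood tests (renal and liver function, electrolytes, lipid profile, NTproBNP/BNP, CA125, blood count, and coagulation)". The same panel is repeated at discharge and at both clinic visits (sections 5.5.3 to 5.5.5). Section 5.2 also makes an admission NT-proBNP or BNP value an entry criterion.

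For the biomarkers the protocol names no baseline-adjusted model, no transformation and no responder cut-off.

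**The concern.** The two sections do not name the same quantity: one gives a proportional change, the other levels. These are different comparisons with different precision.

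Whichever is meant, every test on the list is unadjusted. The qualifier that lets the analyst pick a suitable test therefore cannot lead to an analysis that conditions on the admission value. A chance imbalance in admission values carries into the result, and variation that the admission value could explain stays in the error term.

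Proportional change is also an awkward scale for a t-test. It cannot fall below −100% but has no upper limit, so a few large rises can dominate the mean. Chi-square and Fisher's test could be used on a biomarker only after dichotomising it, and no cut-off is given for that.

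At stake is the precision and clarity of the answer to hypothesis 2.2. The primary endpoint is not affected.

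**Working it through.** **Plan's own figure.** The protocol states no power or precision for the biomarkers, so there is none to reproduce. Its one sample size, 507 per group, is for the primary clinical endpoint and is used here only as a head count.

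**Inputs from the protocol.** 507 per group, 10% loss and 5% significance (section 5.6); 1:1 allocation (section 5.4). Evaluable patients: 507 × 0.9 ≈ 456 per arm.

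**Assumed inputs.** A two-sided test, log-normal markers with equal variance σ² at both times, log-scale SD σ = 1, a true effect of 0.15 log units (ratio e^−0.15 ≈ 0.86), and a correlation ρ of 0.3 to 0.8 between admission and follow-up on the log scale.

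**Step 1: variances on the log scale, per patient.**
- Change from admission: 2(1−ρ)σ²
- Follow-up level alone: σ²
- ANCOVA adjusted for admission: (1−ρ²)σ²

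ANCOVA relative to change is (1−ρ²) / [2(1−ρ)] = (1+ρ)/2. Relative to the follow-up level it is 1−ρ².

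**Step 2: power.** Power = Φ(0.15/√(2V/456) − 1.96), where V is the variance from step 1. For ρ = 0.3:
- Change: V = 1.40, standard error √(2.80/456) = 0.0784, power Φ(1.914 − 1.96) = 48.2%.
- ANCOVA: V = 0.91, standard error √(1.82/456) = 0.0632, power Φ(2.374 − 1.96) = 66.1%.

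| ρ | ANCOVA/change variance | ANCOVA/level variance | Power: log change | Power: level | Power: ANCOVA |
|---|---|---|---|---|---|
| 0.3 | 0.65 | 0.91 | 48.2% | 62.0% | 66.1% |
| 0.5 | 0.75 | 0.75 | 62.0% | 62.0% | 74.4% |
| 0.7 | 0.85 | 0.51 | 83.2% | 62.0% | 88.7% |
| 0.8 | 0.90 | 0.36 | 94.8% | 62.0% | 96.5% |

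The two wordings in the protocol diverge: below ρ = 0.5 the level comparison is the stronger, above it the change comparison is. ANCOVA is better than both at every ρ shown.

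Put another way, an effect for which the log-change test has 80% power gives ANCOVA 93.5%, 89.9%, 86.0% and 84.0% at the four values of ρ.

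**Step 3: the listed tests on raw proportional change.** These were simulated with the same inputs, 1,500 trials per setting:

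| ρ | t-test | Wilcoxon | Chi-square (illustrative 30% fall) | Log ANCOVA | ANCOVA minus Wilcoxon |
|---|---|---|---|---|---|
| 0.3 | 27% | 46% | 33% | 65% | 19 points |
| 0.5 | 43% | 59% | 41% | 75% | 16 points |
| 0.7 | 71% | 81% | 63% | 89% | 8 points |
| 0.8 | 91% | 94% | 81% | 96% | 2 points |

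Proportional change is a monotone function of log change, so Wilcoxon gives the same result on either. Its simulated power does sit just below the log-change column of step 2.

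**Step 4: a second set of assumptions.** With 400 per arm, log SD 0.9 and a ratio of 0.85, Wilcoxon against log ANCOVA gives 64% and 79% (ρ = 0.4), 77% and 88% (ρ = 0.6), and 89% and 95% (ρ = 0.7). The gains are 15, 11 and 6 points.

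**Step 5: validity.** With no true effect, simulated type I error was about 3% to 6% for all methods. The listed tests are not biased; they are less precise.

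**The case against.** The case on the other side is strong on several points.

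- **The list of tests may be a menu by variable type.** The sentence opens with secondary outcomes in general, and these include NYHA class and the components of the primary endpoint, for which chi-square and Fisher's test are right. A reader might infer that the trial will run chi-square on a continuous marker, or a t-test on skewed data. The sentence does not commit it to either, and Wilcoxon is available. The fair comparator is therefore Wilcoxon. What stands is that no item on the menu adjusts for the admission value.
- **The admission value is not ignored.** A reader might infer that it is. Under section 5.3 it is the denominator of the endpoint. The narrower point holds: the comparison is not adjusted for it.
- **Pooling of assays.** A reader might infer that NT-proBNP and BNP will be analysed as one variable. The protocol never says so: section 5.3 uses a class name, section 5.2 gives separate thresholds, and proportional change has no units. The assay needs care in the model proposed here, but it is no error in the plan.
- **SAP content.** Transformations and covariates are often left to the SAP, which is not at hand and may add them. That would answer a complaint about missing detail. Here, however, the protocol does name the tests and the metric, in words that do not match, so there is text to correct.
- **Size.** The protocol gives no SD, correlation or target difference, so a substantial loss of power cannot be read from it. This stands in full.

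**Conclusion.** The point holds as a minor improvement to a secondary endpoint. Sections 5.3 and 5.6 describe the tested quantity differently, and section 5.6 offers only unadjusted tests although the admission value is collected. Those tests remain valid under randomisation; the cost is precision and, if a t-test on raw percent change were chosen, sensitivity to outliers.

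The variance ratio (1+ρ)/2 against an unadjusted log-change test is algebra, given equal log-scale variances at the two times. Its value, 0.65 to 0.90, depends on an assumed ρ of 0.3 to 0.8. The gain of about 2 to 19 points over Wilcoxon depends also on the assumed SD, effect and number evaluable. If ρ is high the gain over Wilcoxon is small. The larger gaps against a t-test on raw percent change, or against a dichotomised chi-square, should not be presented as the expected loss, because the plan does not require those tests.

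A reader might extend the argument to covariate adjustment of the primary Cox model. Nothing here supports that: section 5.6 does not say whether the Cox model is adjusted, the calculation concerns biomarkers only, and adjustment would change the hazard ratio being estimated.

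**What to change.** 1. State the biomarker endpoint in the same terms in sections 5.3 and 5.6.
2. Name as the main analysis an ANCOVA of log(first post-discharge value) on treatment and log(admission value), with one model per marker. Analyse NT-proBNP and BNP separately, or include a term for assay type.
3. Report the adjusted ratio of geometric means with its 95% confidence interval.
4. Keep Wilcoxon on proportional change as a sensitivity analysis, and say that chi-square and Fisher's test are for categorical outcomes such as NYHA class.

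No new data, visits or patients are needed. The cost is administrative: section 5.13 classes a change that affects data analysis as substantial, so ethics committee approval is required before it takes effect. It is best done before the first interim analysis at 30% of the sample, since section 5.8 plans to look at efficacy variables then.
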